## **6.5 Randomisation**

Patients will be randomly assigned to two groups according to the product under study or control product (two interventions considered as standard clinical practice based on the suspicion of aetiology associated to the VV). Random assignment of patients will be implicit in the code that will be assigned to them consecutively in each centre at the time of inclusion. The proportion of patients will be 1:1 between the study group and control group. Random lists will be generated with a software using blocks with up to three repetitions of the same treatment.

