## **6.8 Pre-determination of sample size**

A minimum of 50 patients are expected to be distributed between the study group (boric acid 150 mg, *L. gasseri*, *L. rhamnosus*) and control group (Clotrimazole 100 mg or Clindamycin 100 mg).

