### **8.2 Objectives of the study**

The analysis of the main objective will focus on the comparison of the effectiveness of the product under study (boric acid + *L. gasseri* and *L. rhamnosus*) and that of the control treatment with solid vaginal forms, according to the usual clinical practice (clotrimazole or clindamycin) and assessed according to the patient's clinical symptom scores (VAS, Sobel score) approximately 2 weeks after the end of the treatment. To do this, T tests for independent samples or non-parametric Mann–Whitney U tests will be used.

For the secondary objectives, the level of restoration of vaginal flora will be assessed by comparing the *Lactobacillus* count in baseline discharges and 2 weeks after treatment through T tests for related samples or non-parametric

Wilcoxon or McNemar tests. The incidence of recurrences/relapses at 3 months will be studied by means of proportion comparison tests (Pearson's chi-squared test). The characterisation of the different symptomatic and microbiological profiles of VV, as well as the tolerability, compliance and adverse events, will be analysed through descriptive statistics.

The possibility of carrying out additional analyses, depending on the results, with the relevant statistical tests in each case is not ruled out.

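### Codes are allocated within centre, but the between-arm tests in section 8.2 ignore centre, so they will be somewhat conservative if centres differ

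*Combined protocol and SAP*

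**What the plan says.** On allocation, section 6.5 (Randomisation) refers to a "code that will be assigned to them consecutively in each centre at the time of inclusion". It adds "Random lists will be generated with a software using blocks with up to three repetitions of the same treatment" and "The proportion of patients will be 1:1 between the study group and control group". Read together, this is allocation within centre, although stratification by centre is never named. Section 6.4 describes the code as following the sequence in which patients enter the trial and does not mention centre.

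On analysis, section 8.2 compares symptom scores (VAS, Sobel score) about two weeks after treatment: "To do this, T tests for independent samples or non-parametric" Mann–Whitney U tests. The incidence of recurrence at three months "will be studied by means of proportion comparison tests", namely Pearson's chi-squared. The *Lactobacillus* comparison is paired before and after treatment, so it is not a between-arm test and is not affected here. No centre term, stratified test or mixed model appears in section 8. Further analyses are left open, to be chosen in the light of the results.

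On size, section 6.8 says only "A minimum of 50 patients are expected to be distributed", with no alpha, power, effect size or standard deviation.

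**The concern.** When arms are balanced inside each centre, a centre that scores high or recruits more severe cases adds almost equally to both arms, so its effect largely cancels from the treatment difference. A two-sample test does not know this. It estimates the error from the total spread, including the spread between centres, and so reports a standard error that is too large.

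The documents give no figure for differences between centres, but such differences are plausible. The trial is open, investigators grade erythema and oedema by eye (sections 6.3.3 and 7.1), settings include outpatient and emergency clinics (section 5), and the mix of candidal and bacterial cases may vary by site. At stake are intervals wider than they need be, and some power, in a trial of about 50 patients. Because section 8.2 leaves extra analyses open, a centre adjustment added after the data are seen would also look data-driven.

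**Working it through.** **Inputs from the documents.** Minimum 50 patients in total (6.8); 1:1 ratio, codes consecutive in each centre, blocked lists (6.5); competitive recruitment, hence probably unequal centres (6.3.1); t or Mann–Whitney test and Pearson's chi-squared (8.2).

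**Assumptions.** Two-sided alpha 0.05; outcome SD 1; effect about 0.8 SD; between-centre variance share (ICC) 0 to 0.3; 3 to 10 centres; blocks of 6. A control-arm recurrence rate of 30% is assumed for the chi-squared check.

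**The plan's own figure.** The 50 cannot be reproduced, because no inputs are given. For orientation, 25 per arm has 80% power for (1.96 + 0.8416) × √(2/25) = 0.79 SD, and 80.7% power for 0.8 SD.

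**Step 1: large-sample size of the unadjusted test.** With full balance within centres, the arm difference has variance proportional to 1 − ICC, while the unadjusted test uses a variance proportional to 1. So

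true size = 2 × [1 − Φ(1.96 / √(1 − ICC))].

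| ICC | √(1 − ICC) | True size |
|---|---|---|
| 0 | 1.000 | 5.0% |
| 0.05 | 0.975 | 4.4% |
| 0.10 | 0.949 | 3.9% |
| 0.20 | 0.894 | 2.8% |
| 0.30 | 0.837 | 1.9% |

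**Step 2: simulation at 50 patients, six unequal centres** (5,000 runs per setting; Monte Carlo SE about 0.3 points for size). Power is at 0.8 SD.

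| ICC | Size, t | Size, Mann–Whitney | Size, t with fixed centre terms | Power, t | Power, t with fixed centre terms |
|---|---|---|---|---|---|
| 0 | 5.3% | 5.2% | 4.9% | 78.6% | 77.2% |
| 0.05 | 4.7% | 4.8% | 4.8% | 80.6% | 80.0% |
| 0.10 | 4.0% | 4.2% | 4.6% | 79.7% | 81.1% |
| 0.20 | 3.7% | 4.0% | 5.2% | 81.4% | 85.7% |
| 0.30 | 3.0% | 3.1% | 5.1% | 84.9% | 90.9% |

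Five centres of ten patients give much the same. At ICC 0.1, 0.2 and 0.3 the t test's size is 4.0%, 3.2% and 2.6%. Power at 0.81 SD is 82%, 83% and 84% unadjusted against 84%, 87% and 91% adjusted. The simulated sizes lie above most of the large-sample values because incomplete blocks leave some imbalance and a handful of centres shows, on average, less spread than the assumed share.

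**Step 3: the estimate itself.** With six centres and no treatment effect, the empirical SD of the estimated difference is 0.269 unadjusted and 0.271 adjusted at ICC 0.1, and 0.243 and 0.241 at ICC 0.3. The estimate is almost equally precise either way. What is wrong is the standard error reported for it.

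**Step 4: recurrence** (six centres of 22, 10, 6, 5, 4 and 3 patients; 8,000 runs). For centre SDs of 0, 0.5, 1.0 and 1.5 on the logit scale, Pearson's test has size 5.7%, 5.3%, 4.4% and 3.4%; the Mantel–Haenszel test stratified by centre has 5.2%, 5.0%, 5.0% and 5.0%. At a log odds ratio of −1.5, power is 50.3%, 49.2%, 45.8% and 40.5% for Pearson against 47.1%, 47.7%, 46.6% and 45.1% stratified. The gain therefore appears only when centres differ strongly.

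**Step 5: many small centres.** With ten small centres and fixed centre terms, power at 0.8 SD is 75.1% adjusted against 80.7% unadjusted at ICC 0, 77.5% against 80.3% at 0.1, and 87.6% against 84.2% at 0.3. With ten centres of 14, 10, 7, 5, 4, 3, 2, 2, 2 and 1 patients, power at 0.81 SD is 74.7% against 79.5% at ICC 0. Pooling all centres with fewer than six patients cuts that loss to about 1 point.

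**Step 6: a single central list.** With six centres, the unadjusted t test keeps its size: 5.3% at ICC 0.1 and 4.8% at ICC 0.3.

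**The case against.** Four arguments can be made for leaving the plan alone.

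- **It depends on centres differing.** The documents give no between-centre variance. With none, the unadjusted tests are correctly calibrated, and at a 5% share the change is negligible. This stands, and limits the point to a conditional one.
- **Adjustment can cost more than it gains.** With many small centres and fixed centre terms it does, at low shares (step 5). The list of centres is not in the text available for review, so its length cannot be checked, and that absence is no fault of the plan. This stands against unpooled fixed terms, but pooling or a random centre effect answers most of it.
- **The lists may not run per centre.** Section 6.4 can be read as one trial-wide sequence. Under that reading the tests keep their size. The wording of 6.5 is the more specific, but the two sections must be reconciled.
- **This is a declared pilot with no stated power target.** That lowers the importance of a few points of power. Even so, a pilot's main product is an estimate with a sound interval, and the interval is what is affected.

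A reader might infer that ignoring centre makes the tests invalid or produces false positives. The calculations show the opposite direction: size falls as centres differ more. The 5.7% for Pearson's test arises with no centre effect at all, so ignoring centre is not its cause. Nor does the treatment estimate become biased or markedly less precise, since balance within centres already protects it (step 3).

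**Conclusion.** The point holds as a conditional matter of efficiency and correct standard errors; it does not threaten the trial's validity. The analysis omits a factor that section 6.5 appears to use in allocation. If centres differ, reported standard errors are too large and all three between-arm tests are conservative. At 50 patients and five or six centres, the t test's true size is about 4% at an assumed between-centre share of 10%, 3 to 4% at 20% and 2.5 to 3% at 30%. The corresponding power loss is about 1 to 2, 4, and 6 to 7 points. At 5% or less nothing of practical note is lost.

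These figures rest on assumed values for the between-centre share, number and sizes of centres, block size, alpha and effect size, and on allocation running within centre. A definite loss of power cannot be claimed from the documents. What can be claimed is that analysis and allocation do not match, and that the mismatch is cheap to remove before the data are seen.

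**What to change.** 1. In sections 6.4 and 6.5, state in the same terms whether each centre has its own blocked list.
2. In section 8.2, pre-specify a centre-adjusted main analysis: a linear model for the V1 score with arm and centre. If a rank test is needed, use a Wilcoxon test stratified by centre (van Elteren). For recurrence, use a Mantel–Haenszel comparison stratified by centre.
3. Fix in advance a rule that pools all very small centres into one stratum, for example those with fewer than six patients and not only those with patients in one arm. Alternatively, use a random centre effect in the score model.
4. Keep the unadjusted t, Mann–Whitney and chi-squared tests as sensitivity analyses.

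The change takes a few sentences and needs no new data. If centres turn out not to differ, it costs about 1 point of power for the score comparison with small centres pooled, and about 5 points with many small centres left unpooled. For recurrence, the stratified test was about 3 points lower in power with no centre effect (47.1% against 50.3%), part of which reflects Pearson's slightly raised size in that setting.

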Among the different treatment alternatives for infectious VV, the use of boric acid has been described as an effective, well-tolerated and particularly useful therapeutic option in the case of recurrent VV and candidiasis associated with non-albicans *Candida*. Most studies with vaginal boric acid have studied its administration at doses of 600 mg.

Boric acid is considered a topical action agent that, by combining its bacteriostatic, fungistatic and fungicidal properties, has shown effective results in the control of infectious VV symptoms. Although its mechanism of action is not clearly defined, a potential inhibitor effect of fungal oxidative metabolism that favours the properties previously described has been proposed.

In addition, many studies have been carried out in recent years that show positive results regarding the use of probiotics in patients with VV of infectious origin. The use of these products in the treatment of infectious VV is based on the role of *Lactobacillus* as bacterial flora, maintaining a vaginal pH that promotes balance in the vaginal microenvironment, controlling the growth of potential pathogens that cause VV and reducing the possibility of overcolonisation by *Candida*. There is little evidence available regarding the simultaneous use of antiseptics such as boric acid with probiotics to treat this type of patients.

*De Seta and col.* carried out a comparative study of conventional therapies for BV (Clindamycin) and VC (clotrimazole) and a combination of boric acid with probiotics (*Lactobacillus sp.*) in which a better concentration of lactobacilli was observed in the group treated with boric acid + probiotics 3 weeks after completing the treatment. These patients also registered a significant improvement in symptoms such as stinging, itching, the presence of leukorrhea and fetid vaginal discharge.

For all these reasons, the combination of boric acid with probiotics is postulated as a potential therapeutic alternative for the treatment of infectious VV, which

may end up being incorporated into the usual therapeutic arsenal against VV, and should therefore be compared to other current reference treatments in daily clinical practice.

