#### **3.2 Secondary objectives**

- To determine the incidence of recurrence/relapse at 3 months.
- To assess the level of post-treatment vaginal flora restoration.
- To characterise the different symptomatic and microbiological profiles of VV.
- To assess the tolerance and safety of the product.

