### 6.3.3 Baseline Visit – $V_0$ (inclusion)

After the case history and initial examination, which will serve to substantiate the suspicion of VV due to infection, patients will be recommended to participate in the trial provided they meet the inclusion/exclusion criteria. Once the patient Information Sheet (PIS) has been handed over, the patient has signed the Informed Consent (IC) form and the investigator has verified that the patient meets the inclusion and exclusion criteria, they will proceed to fill in the CRF baseline visit sections.

During this first visit, socio-demographic data, relevant clinical history and gynaecological history will be recorded. The investigator will assess the patient's symptoms by recording the presence of clinical signs and symptoms of infectious VV (stinging, itching, erythema, oedema, abnormal vaginal discharge, etc.) and the *Sobel score* (see section 7.0). The vaginal pH determination test will then be carried out and the samples for the different laboratory tests will be collected, which will consist of: spreading the vaginal discharge sample on a slide to subsequently count the *Lactobacillus spp.* and collecting the discharge sample with a swab that will also be used for the diagnostic confirmation culture and for the fresh vaginal smear. The samples will be stored properly according to the instructions specified in the manual of use of the sampling kit until the samples are collected.

The patient will be given the treatment corresponding to the code assigned to her, reminding her that she has the possibility of changing treatment group, at the time that she deems appropriate. If the assigned treatment is ineffective or

is not tolerable, the patient may contact the hospital to bring the first control visit forward and request a change of treatment.

During the baseline visit, the patient will be given a CRF which she must fill in and return at the end of the visit and a card with a link to the online home CRF (Patient diary) that must be filled in over the course of the study. The home CRF will be used to monitor the patient during the follow-up weeks. The home CRF may also be delivered on paper and the patient must deliver it later.

The investigator will give the patient product for one treatment cycle (which may range from 3 days (Clindamycin) to 7 days (boric acid 150 mg, *L. gasseri*, *L. rhamnosus*)).

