### 7.3 End points

- Number of patients with VV recurrence during the follow-up period in each treatment group (incidence of recurrences after 3 months).
- Number of patients with resolved symptoms in each group 2 weeks after finishing the treatment.
- Changes in vaginal pH level in each group.
- Number of patients with “*clue cells*” or hyphas in the fresh smear.

- Profile and proportion of pathogen isolation in culture.
- Increase in the population of *Lactobacillus spp.* post-treatment.
- Rescue success rate in different scenarios.
- Relationship between compliance and treatment effectiveness.
- Relationship between compliance and recurrence after 3 months.
- Percentage of cases with good treatment tolerability.
- Rate of adverse events.
- Treatment tolerability.
- Proportion of patients with mixed infections (VC + BV).

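### Section 8.2 tests flora restoration only before versus after treatment and pre-specifies no between-arm comparison of the Lactobacillus count

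*Combined protocol and SAP*

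**What the plan says.** The secondary objective in section 3.2 is "To assess the level of post-treatment vaginal flora restoration", with no comparator named. The matching end point in section 7.3 is "Increase in the population of *Lactobacillus spp.* post-treatment". It carries no reference to groups, whereas the pH end point in the same list reads "Changes in vaginal pH level in each group".

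For the analysis, section 8.2 compares the Lactobacillus "count in baseline discharges and 2 weeks after treatment through T tests for related samples or non-parametric" Wilcoxon or McNemar tests. It does not say whether this is done within each arm or in all patients together. In the same section the symptom scores are compared between arms ("To do this, T tests for independent samples or non-parametric" Mann–Whitney tests), and recurrence at 3 months gets a chi-squared comparison of proportions.

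The data for an arm comparison are planned. At V0 the procedures include "spreading the vaginal discharge sample on a slide to subsequently count the" lactobacilli (section 6.3.3), and section 6.3.5 repeats the tests and samples at V1. Section 7.1 lists the count among the main assessment variables. Allocation is 1:1 (section 6.1).

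The rationale in section 2 rests partly on a comparative study in which "a better concentration of lactobacilli was observed in the group treated with boric acid + probiotics 3 weeks after completing the treatment".

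**The concern.** A before/after test asks whether the count changed. It does not ask whether the product changed it more than clotrimazole or clindamycin did. Every woman is enrolled with clinical manifestations of infection (section 6.2.1), so a later rise may reflect clearance of infection by any active treatment, natural recovery or regression to the mean. Randomisation separates these from a product effect only if the arms are compared.

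If the paired test is pooled, it can detect a real rise but says nothing about product versus control. If it is run per arm, readers will be tempted to set one p-value against the other. Either way, the planned analysis contains no estimate of what the product adds to flora restoration, which is the kind of between-group finding that section 2 cites in its favour.

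**Working it through.** **Is a between-arm test of the count planned anywhere?**
- Section 8.2, flora sentence: paired tests only.
- Section 8.2, main objective: independent-samples tests, but for VAS and Sobel scores only.
- Section 8.1: descriptive statistics for all CRF variables, without saying by arm and without a difference or interval.
- Section 8.2, closing sentence: further analyses are possible but depend on the results, so nothing is pre-specified.

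No section supplies the comparison.

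**Inputs.** The only sample-size figure is the minimum of 50 in section 6.8. It comes with no alpha, power, effect size or SD, so it cannot be reproduced. At 1:1 it gives 50/2 = 25 per arm. My assumptions are two-sided 0.05, 25 evaluable patients per arm, normally distributed changes, and the same true rise g in both arms (no product effect), with g in SDs of within-patient change.

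**What per-arm paired tests would show.** Let u be the chance that one arm shows a significant rise: u = P(T > 2.064), where T is noncentral t with 24 df and noncentrality g√25. The chance that only the product arm is significant is u(1 − u).

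| g (SD) | u | u(1 − u) |
|---|---|---|
| 0.3 | 0.302 | 0.211 |
| 0.4 | 0.484 | 0.250 |
| 0.6 | 0.821 | 0.147 |
| 0.8 | 0.970 | 0.029 |

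At g = 0.4 the noncentrality is 0.4 × 5 = 2.0, and 0.484 × 0.516 = 0.250. A valid between-arm test would favour the product in 0.05/2 = 2.5% of trials at every g.

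**Pooled paired test.** With n = 50 and g = 0.4, a significant rise appears with probability 0.79, although the product adds nothing over control.

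**Unequal spread.** The control arm mixes two drugs, so its SD may differ. If the raw rise is the same but the control SD is 1.25 times larger (assumed), a rise of 0.5 SD in the product arm is 0.5/1.25 = 0.4 SD in the control arm. The chance that only the product arm is significant is then 0.670 × (1 − 0.484) = 0.346.

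**Precision of an arm comparison at 25 per arm**, in SDs of the outcome compared:
- 95% CI half-width, unadjusted: 2.011 × √(2/25) = 2.011 × 0.283 = 0.57 SD.
- Difference detectable with 80% power: 0.81 SD (noncentral t).
- With an assumed correlation of 0.5 between V0 and V1 counts, adjustment multiplies this by √(1 − 0.5²) = 0.866, giving 0.70 SD.

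**Timing of the V1 sample.** Section 6.3.3 describes "one treatment cycle (which may range from 3 days (Clindamycin) to 7 days" for the study product, and section 1.16 gives 6 days for clotrimazole. Section 6.3.4 puts V1 at 21 days from V0. If the first dose is on the day of V0 (day 0), the last doses fall on days 6, 5 and 2, so V1 comes 15, 16 and 19 days after the last dose of study product, clotrimazole and clindamycin. Sections 6.3.3 and 6.3.5 instead time V1 from the end of treatment, and section 6.3.4 lets it move for menstruation. The actual intervals therefore have to be observed.

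**The case against.** The strongest reply is that the plan is internally consistent. The objective and end point ask about restoration after treatment, and a paired test answers that. This is a secondary end point in a declared pilot, and Lactobacillus is better served than pH, for which section 8.2 names no inferential test. That stands, and it limits the weight of the point. It does not remove it: the recurrence objective in section 3.2 is also worded without a comparator, yet section 8.2 gives it a comparison of proportions.

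Three stronger readings are tempting, and the documents support none of them.
- A reader might infer that the plan contradicts its own objective. It does not, because neither objective nor end point is worded as a comparison.
- A reader might infer that the randomised counts will go unused, or that no estimate by arm can appear. Sections 8.1 and 8.2 leave room for both descriptive summaries by arm and later analyses. What can be said is that the comparison is not pre-specified.
- A reader might take 25% as an error rate of the plan, or as a ceiling. It is neither. It describes a misreading that arises only if the tests are run per arm and someone then compares the p-values, and the documents commit to neither. It is a maximum only with equal arm sizes and equal standardised rises; the unequal-SD case above gives about 35%.

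**Conclusion.** The point holds as a gap in pre-specification. Section 8.2 plans only paired tests of the Lactobacillus count, leaves open whether they are pooled or per arm, and names no comparison of the randomised arms, although the counts are collected in both. A before/after rise in symptomatic women cannot be credited to the product.

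The illustration (about 25% against 2.5% at a common rise of 0.4 SD) rests on assumed alpha, normality, equal SDs and 25 evaluable patients per arm. At a common rise of 0.8 SD it falls to about 3%. The gap itself does not depend on these figures. It should be corrected, but it concerns a secondary end point of a pilot and does not threaten the main symptom comparison.

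**What to change.** In section 8.2:
1. Add a comparison by randomised arm of the V1 Lactobacillus count, adjusted for the original V0 count taken at inclusion before any study treatment. Report the difference with a 95% CI. A simpler alternative is Mann–Whitney, already named in 8.2, on the V0-to-V1 change. Fix the scale of the count before data are seen, since naming both a t test and McNemar leaves it open.
2. Keep the paired before/after results, shown by arm, as description.
3. For patients who cross over, keep the original V0 as baseline. Do not let the reset V0 of sections 6.2.3 and 6.3.5 replace it, because a sample taken after the first treatment would then become a baseline. Report their number per arm, and state before data are seen how their post-treatment value is handled. An on-treatment sample from the switch visit should not be the main value. Section 6.2.3 allows a switch for worsening at 3–4 days, within the 7-day study course, and the capsule contains lactobacilli (section 1.8). Such a sample may count delivered bacteria in one arm only and favour the product.
4. Report the actual days from last dose to the V1 sample by arm.

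The cost is a short paragraph, with no new samples, visits or patients. Item 4 needs a last-dose date, which may mean one CRF field if none exists. The crossover rule takes some thought. The downside is low precision, about ±0.57 SD unadjusted at 25 per arm, so the text should call the result an estimate and not a confirmatory test.

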### *6.2.3 Rescue criteria*

In cases where the patient requires "rescue treatment", the treatments will be crossed. In the event of changing treatment group (crossover), the patient will be considered to be back at V0 and the tests/examinations corresponding to the baseline visit will be repeated.

The patient will change group to receive alternative treatment in the following cases:

- Patient with hypersensitivity to the first assigned treatment.
- Worsening of symptoms within 3-4 days of starting the assigned treatment.
- Evidence or indications of lack of effectiveness after the first assigned treatment.
- Patient who demonstrates a willingness to change treatment.
- In cases where the perceived lack of effectiveness is associated with a suspected mixed aetiology infection (candidal and bacterial):
  - If they are in the control group, they will be changed to the treatment under study (boric acid + *L. gasseri* and *L. rhamnosus*).
  - If they are in the study group, they will be changed to the antifungal treatment (Gine-Canesten®; Clotrimazole 100 mg). If this treatment fails, BV will be treated with antibiotic treatment (Dalacin®; Clindamycin 100 mg).

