### 6.3.2 Follow-up period

Follow-up will be 3 months from the inclusion visit ( $V_0$ ). Patients should attend two control visits in person and answer two telephone interviews.

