### 6.3.6 Telephone interview (TI) 8 weeks after the inclusion

Approximately 8 weeks after the baseline visit, the investigator will telephone the patient to interview her, with the main objective of knowing if there are signs of recurrence of VV.

The patient will confirm whether she is regularly filling in the online CRF and that she is not taking/using any products that may interfere with the assessment of the study objectives (see section 6.2.4: Discontinuation criteria).

The investigator will fill in a short form as a summary of the interview and confirm the appointment for the third and last in-person visit (V2). The patient will be reminded that, if the home CRF is completed on paper, she must deliver it during the last visit.

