### 6.3.7 2nd Control Visit (V2)

Three months after the baseline visit, the patient will go to the last control visit, to assess the incidence of VV recurrences during the follow-up period. The investigator will perform, as in all visits, the corresponding case history and examination and will record data on clinical manifestations. This visit does not include taking samples for laboratory tests. If the patient has filled in the home CRF on paper, she must deliver it during this last visit.

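### The only planned test of 3-month recurrence has no rule or place for a woman followed recurrence-free who then misses V2; Kaplan-Meier with censoring would use her follow-up, for a modest gain

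*Combined protocol and SAP*

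**What the plan says.** Recurrence is the first secondary objective (3.2) and the first end point listed in 7.3: "Number of patients with VV recurrence during the follow-up period in each treatment group (incidence of recurrences after 3 months"). The end point is therefore cumulative over follow-up and is not status at the last visit alone.

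Three planned sources bear on it:

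- The 8-week telephone interview is made "with the main objective of knowing if there are signs of recurrence of VV" (6.3.6).
- V2 is held "to assess the incidence of VV recurrences during the follow-up period" (6.3.7).
- The patient diary runs through the study. Section 6.3.3 gives it a general purpose: "The home CRF will be used to monitor the patient during the follow-up weeks".

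On timing, 6.3.2 states "Follow-up will be 3 months from the inclusion visit". Section 6.2.3 adds "In the event of changing treatment group (crossover), the patient will be considered to be back at" V0, and 6.3.5 treats the crossover visit as a new baseline for data and samples.

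In 8.2 the incidence at 3 months "will be studied by means of proportion comparison tests", and the only one named is Pearson's chi-squared; no time-to-event method appears. The documents state no analysis population, no rule for women without V2, no definition of recurrence as against persistence, and no expected dropout.

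**The concern.** A binary 3-month outcome cannot represent partial follow-up. A woman seen free of recurrence at week 8 and not afterwards carries real information, but the chi-squared test can only leave her out or give her a status that nobody observed. The choice is left to the analyst in an open trial.

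Loss could well differ between arms, because women know their treatment and may ask to change it (6.2.3, 6.3.3). If lost women are counted as recurrence-free, the arm that loses more looks better with no true difference. If they are left out while recurrences seen before loss are kept, that arm looks worse. At stake are the estimate and interval for the trial's first secondary objective.

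**Working it through.** **Inputs from the documents.** Section 6.8 gives the sample size: "A minimum of 50 patients are expected to be distributed between the study group" and the control group. With 1:1 allocation (6.5) that is 25 per arm. Follow-up is 3 months (6.3.2), with contacts near weeks 3, 8 and 12 (6.3.4, 6.3.6, 6.3.7). The figure of 50 comes with no alpha, power, effect or dropout, so it cannot be reproduced, and it is not shown to be wrong.

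**Assumed inputs.** Two-sided 5% level, constant recurrence hazard, loss independent of recurrence, and the recurrence and loss rates shown below.

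**Power.** Simulation of 3,000 trials per row, recurrence dated to the week, error about 1 point. Power in %:

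| True recurrence | Loss per arm | Chi-squared, V2 attenders | Chi-squared, known status | Chi-squared, lost = no recurrence | Log-rank |
|---|---|---|---|---|---|
| 40% v 20% | 0 | 34.4 | 34.4 | 34.4 | 33.5 |
| 40% v 20% | 20% | 28.4 | 30.0 | 31.5 | 30.8 |
| 40% v 20% | 30% | 24.5 | 28.6 | 29.8 | 30.2 |
| 50% v 20% | 0 | 64.6 | 64.6 | 64.6 | 63.6 |
| 50% v 20% | 20% | 53.8 | 57.0 | 57.8 | 58.4 |
| 50% v 20% | 30% | 47.5 | 52.7 | 54.5 | 55.3 |

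Known status means V2 attenders plus women with a recurrence recorded before loss.

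- With loss, the log-rank gain over V2 attenders is 2.4 to 7.8 points in these rows. With loss times uniform over 12 weeks, one run of 50% v 20% gave 51% v 58% (20% loss) and 46% v 55% (30% loss), gains of 7 and 9 points. That gives the range of about 2 to 9.
- For 20% v 10% and 30% v 15% the gain is only about 1 to 3 points.
- Over a chi-squared that keeps recurrences seen before loss, the gain is at most about 3 points and often nil.

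**Precision, 50% v 20%.** The standard error of the risk difference in V2 attenders is √[(0.5×0.5 + 0.2×0.8)/m]. At 20% loss m = 20, giving √(0.41/20) = 0.143. At 30% loss m = 17.5, giving √(0.41/17.5) = 0.153. Simulation gave 0.145 and 0.155, against 0.137 and 0.141 for Kaplan-Meier.

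**False difference with equal 40% risk and 10% v 30% loss.** Let loss times be uniform over 12 weeks and let q be the chance that a lost woman's recurrence is recorded before she is lost. If lost women without a recorded recurrence count as recurrence-free, the expected proportion in an arm with loss d is 0.40 − (0.40 − q)d. The false difference is (0.40 − q)(0.30 − 0.10).

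- *Recurrences recorded as they occur:* q = 1 − 0.40/(−ln 0.60) = 1 − 0.40/0.5108 = 0.217. Difference 0.183 × 0.20 = 3.7 points.
- *Recurrences learned only at weeks 3, 8 and 12:* q = (5/12)(1 − 0.60^(3/12)) + (4/12)(1 − 0.60^(8/12)) = (5/12)(0.120) + (4/12)(0.289) = 0.146. Difference 0.254 × 0.20 = 5.1 points.
- *Every recurrence in a woman who misses V2 discarded:* q = 0. Difference 0.40×0.90 − 0.40×0.70 = 8 points.

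Simulated type I error is about 6-7% in the first two cases and about 9% in the third. Log-rank stays at about 5%, even with contact dates only.

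**Direction of bias by rule.** With a true rate of 30% and 30% loss in both arms, the mean estimates are 30% (V2 attenders), 26% (lost counted as no recurrence), 34-35% (known status) and 30% (Kaplan-Meier).

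**The case against.** The strongest reply is that this is a secondary objective in a pilot with a short fixed window, where a comparison of proportions is legitimate and matches the end point. That stands. So does the arithmetic behind it: with complete follow-up nothing is gained, and a chi-squared that counts every recorded recurrence has nearly the same power as log-rank.

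Three stronger readings are tempting, and the documents do not support them.

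- *Women who miss V2 lose recurrences already recorded.* The plan is silent on this, and 7.3 counts recurrence at any time in follow-up. The 8-point figure needs this reading and is therefore an upper bound.
- *The diary has no analytic use.* Section 6.7 uses it for compliance, which 7.3 relates to effectiveness and recurrence, and 8.1 plans descriptive statistics for all CRF variables. What is missing is its use in the comparison of recurrence.
- *Exact onset dates exist from three sources.* Only the call and V2 are expressly about recurrence, and the diary's items are not shown. Dates known only from contacts are interval-censored.

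It is also fair to say that Kaplan-Meier does not cure informative loss, and that a time-to-event analysis needs an origin and a rule for the reset at crossover. Section 6.2.4 keeps women with failed rescue in follow-up, which limits some loss but does not cover others who stop attending.

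**Conclusion.** The point holds in a limited form. Section 8.2 names one binary test, gives no rule for women without V2, and so leaves a choice between lost precision and bias. Neither is large: about 2 to 9 points of power against V2 attenders only for the larger contrasts at 20-30% loss, and a false difference of about 4 to 5 points if loss is 10% v 30% at equal 40% risk. Both vanish with complete follow-up. Every rate here is assumed, since the documents give neither recurrence nor dropout. The bias results also assume loss independent of recurrence. The case for change rests on the missing rule and the estimate more than on power, and the change is worth making because it draws on contacts already planned.

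**What to change.** In 8.2:

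1. Count a recurrence from any source: home CRF, 8-week call, V2 or unscheduled visit. State what separates recurrence from persistence.
2. Date it by diary onset where recorded, and otherwise by the contact at which it was found.
3. Measure time from randomisation, analyse by randomised arm, and censor at last contact.
4. Report Kaplan-Meier recurrence at 3 months per arm and the difference, each with a 95% confidence interval, with a log-rank test.
5. Keep the chi-squared as a supporting analysis, and state how it classifies women without V2.
6. State how the return to V0 after crossover (6.2.3, 6.3.5) affects the 3-month window.

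The cost is analysis wording and one derived date, with no new visits. Whether the diary records onset dates should be checked; if it does not, contact dates suffice for the estimate. The downsides are self-reported onsets in an open trial (tabulate source by arm), interval-censored contact dates, and no protection against informative loss, so numbers and timing of loss should be shown by arm.
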